Appendix C Handling of Human Biological Samples

C 1 Chain of Custody

A full chain of custody is maintained for all samples throughout their lifecycle.

The investigator at each centre keeps full traceability of collected biological samples from the patients while in storage at the centre until shipment or disposal (where appropriate) and records relevant processing information related to the samples whilst at site.

The sample receiver keeps full traceability of the samples while in storage and during use until used or disposed of or until further shipment and keeps record of receipt of arrival and onward shipment or disposal.

Redx or delegated representatives will keep oversight of the entire life cycle through internal procedures, monitoring of study sites, auditing or process checks, and contractual requirements of external laboratory providers.

Samples retained for further use will be stored in the Redx-assigned biobanks or other sample archive facilities and will be tracked by the appropriate Redx Team during for the remainder of the sample life cycle.

C 2 Withdrawal of Informed Consent for Donated Biological Samples

If a participant withdraws consent to the use of donated biological samples, the samples will be disposed of/destroyed/repatriated, and the action documented. If samples are already analysed, Redx is not obliged to destroy the results of this research.

Following withdrawal of consent for biological samples, further study participation should be considered in relation to the withdrawal processes outlined in the informed consent.

The investigator:

- Ensures participant's' withdrawal of informed consent to the use of donated samples is highlighted immediately to Redx or delegate.
- Ensures that relevant human biological samples from that participant, if stored at the study site, are immediately identified, disposed of as appropriate, and the action documented.
- Ensures that the participant and Redx are informed about the sample disposal.

Redx ensures the organization(s) holding the samples is/are informed about the withdrawn consent as soon as reasonably possible and that samples are disposed of or repatriated as appropriate, and the action documented and study site notified.

C 3 International Airline Transportation Association (IATA) 6.2 Guidance Document

LABELLING AND SHIPMENT OF BIOHAZARD SAMPLES

International Airline Transportation Association (IATA)
(<https://www.iata.org/whatwedo/cargo/dgr/Pages/download.aspx>) classifies infectious substances into 3 categories: Category A, Category B or Exempt

Category A Infectious Substances are infectious substances in a form that, when exposure to it occurs, is capable of causing permanent disability, life-threatening or fatal disease in otherwise healthy humans or animals.

Category A pathogens are e.g., Ebola, Lassa fever virus. Infectious substances meeting these criteria which cause disease in humans or both in humans and animals must be assigned to UN 2814. Infectious substances which cause disease only in animals must be assigned to UN 2900.

Category B Infectious Substances are infectious Substances that do not meet the criteria for inclusion in Category A. Category B pathogens are e.g., Hepatitis A, C, D, and E viruses. They are assigned the following UN number and proper shipping name

- UN 3373 – Biological Substance, Category B
- are to be packed in accordance with UN3373 and IATA 650

Exempt - Substances which do not contain infectious substances or substances which are unlikely to cause disease in humans or animals are not subject to these Regulations unless they meet the criteria for inclusion in another class.

- Clinical study samples will fall into Category B or exempt under IATA regulations
- Clinical study samples will routinely be packed and transported at ambient temperature in IATA 650 compliant packaging
(<https://www.iata.org/whatwedo/cargo/dgr/Documents/DGR-60-EN-PI650.pdf>).
- Biological samples transported in dry ice require additional dangerous goods specification for the dry-ice content
- Files would remain physically separate.

Appendix D

RECIST 1.1 (Response Evaluation Criteria in Solid Tumours) Responses

Term	Definition
Complete response (CR)	Disappearance of all target lesions. Any pathological lymph nodes must have reduction in short axis to <10 mm.
Partial response (PR)	A $\geq 30\%$ decrease in the sum of diameters of target lesions, taking as reference the baseline sum diameters.
Progressive disease (PD)	At least a 20% increase in the sum of diameters of target lesions, taking as reference the smallest sum on study (this includes the baseline sum if that is the smallest on study). In addition to the relative increase of 20%, the sum must also demonstrate an absolute increase of at least 0.5 cm. The appearance of one or more new lesions is also considered progression.
Stable disease (SD)	Neither sufficient shrinkage to qualify for PR nor sufficient increase to qualify for PD, taking as reference the smallest sum diameters while on study.
New lesions	Always represents progressive disease (PD)

Appendix E Prohibited CYP3A4 Inhibitors and Inducers

CYP 3A4 Inhibitors [Bold text denotes commonly used co-medications in patients with pancreatic or biliary tract cancers]	CYP 3A4 Inducers [None of these drugs are commonly used co-medications in patients with pancreatic or biliary tract cancers]

Strong CYP 3A4 Inhibitors Concomitant use of these drugs has the potential to increase the exposure of RXC004 >5-fold These agents must not be given within 14 days of first dose of study treatment
 
Boceprevir, cobicistat, danoprevir and ritonavir, elvitegravir and ritonavir, grapefruit juice, indinavir and ritonavir, itraconazole, ketoconazole, lopinavir and ritonavir, paritaprevir and ritonavir and (ombitasvir and/or dasabuvir), posaconazole, ritonavir, saquinavir and ritonavir, telaprevir, tipranavir and ritonavir, troleandomycin, voriconazole, clarithromycin, idelalisib, nefazodone, nelfinavir.
	
Strong CYP 3A4 Inducers Concomitant use of these drugs has the potential to decrease the exposure of RXC004 by >80% These agents must not be given within 14 days of first dose of study treatment
 
Aptalutamide, carbamazepine, enzalutamide, mitotane, phenytoin, rifampin, St. John's wort.

Moderate CYP3A4 Inhibitors Concomitant use of these drugs has the potential to increase the exposure of RXC004 by 2-5-fold A washout period of 14 days is recommended and a minimum washout period of 5 half-lives (See SMPC or USPI) is required before first dose of study treatment.
 
Aprepitant, , conivaptan, crizotinib, cyclosporine, diltiazem, dronedarone, erythromycin, fluconazole, fluvoxamine, imatinib, tosipam, verapamil lansoprazole.
	
Moderate CYP 3A4 Inducers Concomitant use of these drugs has the potential to decrease the exposure of RXC004 by 60-80% A washout period of 14 days is recommended and a minimum washout period of 5 half-lives (See SMPC or USPI) is required before first dose of study treatment.
 
Bosentan, efavirenz, etravirine, phenobarbital, primidone.


Weak CYP3A4 Inhibitors These are not prohibited but should be used with caution as they may increase the exposure of RXC004 by 1.25 -2- fold
 
Chlorzoxazone, cilostazol, cimetidine, clotrimazole, fosaprepitant, istradefylline, ivacaftor, lomitapide, ranitidine, ranolazine, ticagrelor, omeprazole
	
Weak CYP3A4 Inducers These drugs are not prohibited- they have the potential to decrease the exposure of RXC004 by 20-50% which is within the scope of the dose reduction allowances
 
Armodafinil, modafinil, rufinamide

For updated information, please refer to <https://www.fda.gov/drugs/drug-interactions-labeling/drug-development-and-drug-interactions-table-substrates-inhibitors-and-inducers>

Appendix F

RNF43 Mutations (Module 1)

Module 1 will recruit patients with documented RNF43 mutated PDAC.

PDAC patients with the following RNF43 mutations are eligible for Module 1:

Patients with documented LoF RNF43 mutations other than those listed above may be allowed after consultation with Sponsor.

Appendix G Performance Status

G 1 Karnofsky Performance Status

Karnofsky performance status will be assessed for patients in Module 1 (PDAC) at the times specified in the Module 1 schedules of assessments based on the following:

- 100 Normal no complaints
- 90 Able to carry on normal activities. Minor signs or symptoms of disease
- 80 Normal activity with effort
- 70 Care for self. Unable to carry on normal activity or to do active work
- 60 Requires occasional assistance, but able to care for most of his/her needs
- 50 Requires occasional assistance and frequent medical care
- 40 Disabled. Requires special care and assistance
- 30 Severely disabled. Hospitalisation indicted though death non-imminent
- 20 Very sick. Hospitalisation necessary. Active supportive treatment necessary
- 10 Moribund

G 2 ECOG Performance Status

ECOG performance status will be assessed for patients in Module 2 (BTC) at the times specified in the Module 2 schedule of assessments based on the following:

- 0. Fully active; able to carry out all usual activities without restrictions
- 1. Restricted in strenuous activity, but ambulatory and able to carry out light work or work of a sedentary nature (e.g., light housework or office work)
- 2. Ambulatory and capable of self-care, but unable to carry out any work activities; up and about more than 50% of waking hours
- 3. Capable of only limited self-care; confined to bed or chair more than 50% of waking hours
- 4. Completely disabled; unable to carry out any self-care and totally confined to bed or chair
- 5 Dead

Appendix H Pharmacokinetic Parameter Definitions

PARAMETER	DEFINITION
C_{\max}	The maximum observed concentration.
t_{\max}	The time at which C_{\max} was apparent.
AUC_{0-t}	The area under the concentration versus time curve from time zero to the sampling time at the last quantifiable concentration (C_t) at t_{last} (the time of the last quantifiable concentration) calculated by the linear trapezoidal rule.
λ_z	The apparent terminal rate constant, estimated using the negative slope of the least square regression analysis of the log concentration versus time data for the terminal linear portion of the curve.
$t_{1/2}$	The apparent terminal half-life, calculated from $\log_e 2 / \lambda_z$.
$AUC_{0-\infty}$	The area under the concentration-time curve estimated from time zero to infinity as the sum of the two areas: AUC_{0-t} and AUC_{extrap} , where AUC_{extrap} is calculated as C_t / λ_z .
CL	The systemic clearance calculated as: dose/ $AUC_{0-\infty}$.

Abbreviation or special term	Explanation
AE	Adverse Event
AEPI	Adverse Event of Potential Interest
ALT	Alanine aminotransferase
ASCO	American Society of Clinical Oncology
AST	Aspartate aminotransferase
BOR	Best Overall Response
BTC	Biliary tract cancer
CD8	Cluster of differentiation 8
C _{max}	Maximum (peak) observed plasma concentration
C _{min}	Minimum (trough) observed concentration across the dosing interval
CRO	Contract Research Organisation
CCA	Cholangiocarcinoma
CI	Confidence interval
CNS	Central nervous system
COVID-19	Coronavirus disease 2019
CR	Complete response
CRC	Colorectal cancer
CrCL	Creatinine clearance
CSP	Clinical Study Protocol
CSR	Clinical Study Report
CT	Computerised tomography
CTCAE	Common Terminology Criteria for Adverse Events (National Cancer Institute)
CCI	CCI
CTLA-4	Cytotoxic T-lymphocyte-associated protein 4
DBL	Data Base Lock
DCO	Data Cut Off
DCR	Disease Control Rate
DILI	Drug-induced liver injury
CCI	CCI
ECG	Electrocardiogram
ECOG	Eastern Cooperative Oncology Group
ESMO	European Society for Medical Oncology
EU	European Union

Abbreviation or special term	Explanation
eCRF	electronic Case Report Form
FDA	U.S. Food and Drug Administration
CCI	CCI
FFPE	Formalin-fixed, paraffin-embedded
Fz	Frizzled
GCP	Good Clinical Practice
HBV	Hepatitis B
HCV	Hepatitis C
IB	Investigator's Brochure
ICF	Informed Consent Form
IP	Investigational Product
irAE	Immune-related adverse event
IV	Intravenous
LoF	Loss of function
LRP	Low-density lipoprotein receptor-related protein
ORR	Overall Response Rate
OS	Overall survival
PCR	Polymerase chain reaction
PD-1	Programmed cell death protein-1
PDAC	Pancreatic Ductal Adenocarcinoma
PD-L1	Programmed cell death ligand-1
PD-L2	Programmed cell death ligand-2
PFS	Progression-free survival
PI	Principal Investigator
PK	Pharmacokinetic(s)
PORCN	Porcupine
PR	Partial response
QD	Once daily
q[x]w	Every [x] weeks
RECIST	Response Evaluation Criteria In Solid Tumours
RNF43	Ring finger protein 43
RSPO	R-Spondin
SAE	Serious Adverse Event
SAP	Statistical Analysis Plan
SD	Stable disease

Abbreviation or special term	Explanation
SMC	Safety monitoring committee
SmPC	Summary of Product Characteristics
SoA	Schedule of Assessments
SoC	Standard of Care
SRC	Safety review committee [for the Phase 1 study]
Treg	Regulatory T-cell

Appendix J Dysgeusia Treatment Guidelines

As there are no recognised standard international guidelines for the management of this multifactorial event, investigators are advised to consult their local practice guidelines for the management of dysgeusia. Please refer to Table 11, Section 6.5 for instructions on dose reductions and interruptions for dysgeusia.

Some interventions may be effective in treating dysgeusia:

- Treatment with oral pilocarpine and artificial saliva may help in cases where there is also dry mouth
- Zinc supplements may help in cases where there is evidence of zinc deficiency
- Alpha lipoic acid is an antioxidant capsule supplement which may improve flavour sensation
- Good oral hygiene and chlorhexidine (or similar) mouthwashes

Patients may be advised of some ways that they can manage dysgeusia, for example:

- Cooking or eating food in non-metallic cookware
- Avoiding foods that taste bitter or metallic
- Flavoring foods with seasonings and spices
- Eating food cold may help to reduce unpleasant flavor sensations
- Frequently brushing teeth
- Rinsing with mouth wash regularly
- Using chewing gum. Lozenges or mints to stimulate saliva production

A dysgeusia treatment algorithm has been developed by Sevryugin et al 2021 based on their review of published studies of dysgeusia interventions and is included to assist Investigators with the management of dysgeusia that occurs during treatment with RXC004. However, it is acknowledged that not all of the management suggestions may be readily available or applicable to patients in this study.

Figure 2 Dysgeusia Treatment

[figure not shown]

Figure from Sevryugin et al 2021.

Appendix K Management of Colitis Events

In the Phase 1 study of RXC004, events of colitis or enteritis were reported in four patients who commenced treatment at doses of 3 mg QD or 10 mg QD. At the time of publishing this protocol, an SAE of Grade 3 enteritis has been reported in 1 patient out of 12 patients dosed in the Phase 2 study RXC004/0002 and an SAE of Grade 3 colitis has been reported in 1 patient out of 21 patients dosed in this Phase 2 study (RXC004/0003). Both patients were receiving RXC004 2 mg QD. The enteritis and the colitis events were both considered by the Investigator as RXC004-related.

RXC004-related diarrhoea/colitis may present as abdominal pain with other symptoms including intermittent constipation, diarrhoea, nausea and/or vomiting. In some cases, symptoms may be minimal. Blood and mucus in the stool may not be apparent. Symptoms may be preceded by or accompanied by a raised CRP and neutrophil count.

Pembrolizumab is also known to cause irAEs including colitis.

If lower GI-tract inflammation is suspected, infectious and other causes should be excluded, including CMV and *C. difficile*. Attempts should be made to definitively diagnose the condition with a CT scan and colonoscopy/sigmoidoscopy with biopsy, if clinically safe to do so.

Management:

Monitoring of CRP or fecal calprotectin levels may help to monitor the response to treatment.

Table 19 Management of Colitis Events

Event and grade	Management
Grade 1 colitis (asymptomatic but evidence on CT scan)	Continue RXC004 at a lower dose and repeat the CT scan within 4 weeks. No action is needed for pembrolizumab. No additional treatment is indicated. If the Grade 1 colitis is evident on- the second scan despite the lower dose of RXC004, it should be managed as Grade 2 colitis and the scan should be repeated within 4 weeks.
Grade 2 colitis (abdominal pain, mucus or blood in stool)	Pause RXC004 and pembrolizumab (if applicable).

Event and grade	Management
	
Manage with corticosteroids at a dose of 1-2 mg/kg methylprednisolone equivalent.
 
When symptoms have resolved, taper over 2-4 weeks.
 
If symptoms recur during tapering, the steroid dose may need to be increased again.
 
If no improvement in 72 hrs despite treatment, treat as Grade 3.
 
RXC004 can be restarted at a lower dose after colitis has resolved to Grade $\leq 1^*$ and steroids tapered to physiological levels (<10 mg prednisolone per day equivalent dose) over at least 1 month.
 
If steroids cannot be tapered to physiological levels within 12 weeks of commencing steroid treatment, then RXC004 and pembrolizumab (if applicable) should be permanently discontinued.

Grade 3 colitis (severe or persistent abdominal pain, fever, ileus; peritoneal signs)	
Pause RXC004 and pembrolizumab, if applicable.
 
Seek specialist advice.
 
Manage with corticosteroids at a dose of 1-2 mg/kg methlyprednisolone equivalent.
 
When symptoms improve, taper steroids to physiological levels over 4-8 weeks and consider use of prophylactic antibiotics and anti-fungals.
 
RXC004 can be restarted at a lower dose after colitis has resolved to Grade $\leq 1^*$ and steroids tapered to physiological levels

Event and grade	Management
	
(<10 mg prednisolone per day equivalent dose)
 
If steroids cannot be tapered to physiological levels within 12 weeks of commencing steroid treatment, then RXC004 and pembrolizumab, if applicable, should be permanently discontinued
 
Additional anti-inflammatory medications (e.g. infliximab) may be indicated if no improvement in 48-72 hrs. It is important to rule out bowel perforation and refer to infliximab SMPC/USPI for general guidance before using infliximab.
 
If anti-inflammatories are required RXC004 and pembrolizumab, if applicable, should be permanently discontinued.

Grade 4 colitis (life-threatening consequences)	
Manage as Grade 3 colitis.
 
RXC004 and pembrolizumab, if applicable, should be permanently discontinued.

*Attempts should be made to confirm that the colitis has resolved to Grade ≤ 1 (e.g. normalised CRP or fecal calprotectin if raised during event; GI appearance normalised on X ray/ CT or endoscopy) before restarting RXC004.

If there is any recurrence of colitis \geq Grade 2 after recommencing RXC004, **RXC004 and pembrolizumab, if applicable, should be permanently discontinued.**

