6.5.1 Dose Modifications for RXC004

RXC004 dose reduction and interruption are permitted.

RXC004 may be dose interrupted (withheld) until a clinically significant (any grade) and/or a grade ≥ 3 related adverse event resolves to baseline or \leq grade 2. RXC004 may also be withheld if it is necessary to give a concomitant medication that is a moderate or strong CYP3A4 inhibitor.

Colitis events may occur with RXC004 or with pembrolizumab, and should be managed per Appendix K and, for participants in Module 3, the dose modification and toxicity management guidelines for irAEs associated with pembrolizumab (Appendix L 1) if applicable. For patients receiving the combination treatment with RXC004 and pembrolizumab, the most conservative guideline should be followed.

RXC004 dose interruption and stopping criteria are detailed in Table 11.

Table 11 RXC004 Dose Modification and Stopping Criteria

Event	Action
Colitis events (e.g. Colitis, ileitis, enterocolitis etc)	
Grade 1	Reduce RXC004 to a lower dose (see Table 12 for dose reduction scheme) and manage per Appendix K. If receiving RXC004 in combination with pembrolizumab, no additional action is required for pembrolizumab.
Grade 2	Interrupt RXC004. Manage as per Appendix K. When event has resolved to Grade $\leq 1^a$ and steroids have been tapered to prednisolone ≤ 10 mg per day (or equivalent), resume RXC004 at a lower dose (see Table 12 for dose-reduction scheme). If event recurs after re-starting study treatment, then RXC004 should be permanently discontinued. If receiving RXC004 in combination with pembrolizumab, interrupt pembrolizumab and see Appendix L for guidance.
Grade 3	Interrupt RXC004. Manage as per Appendix K. When event has resolved to Grade $\leq 1^a$ and steroids have been tapered to ≤ 10 mg of prednisolone per day (or equivalent), resume RXC004 at a lower dose (see Table 12 for dose reduction scheme). If event recurs after re-starting study treatment, then RXC004 should be permanently discontinued. If receiving RXC004 in combination with pembrolizumab; permanently discontinue both agents and manage as per Appendix K and Appendix L.
Grade 4	If receiving RXC004, either as monotherapy or in combination with pembrolizumab: Permanently discontinue both agents. Manage per Appendix K and Appendix L.
Dysgeusia events	

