Appendix L Pembrolizumab Dose Modification and Toxicity Management

L 1 Dose Modification and Toxicity Management for Immune-related AEs Associated with Pembrolizumab

AEs associated with pembrolizumab exposure may represent an immunological aetiology. These irAEs may occur shortly after the first dose or several months after the last dose of pembrolizumab treatment and may affect more than one body system simultaneously. Therefore, early recognition and initiation of treatment is critical to reduce complications. Based on existing clinical study data, most irAEs were reversible and could be managed with interruptions of pembrolizumab, administration of corticosteroids, and/or other supportive care. For suspected irAEs, ensure adequate evaluation to confirm aetiology or exclude other causes. Additional procedures or tests such as bronchoscopy, endoscopy, or skin biopsy may be included as part of the evaluation. Based on the severity of irAEs, withhold or permanently discontinue pembrolizumab and administer corticosteroids. Dose modification and toxicity management guidelines for irAEs associated with pembrolizumab are provided in Table 20.

Table 20 Dose Modification and Toxicity Management Guidelines for Immune-related AEs Associated with Pembrolizumab

General instructions:	
 Severe and life-threatening irAEs should be treated with IV corticosteroids followed by oral steroids. Other immunosuppressive treatment should begin if the irAEs are not controlled by corticosteroids. Pembrolizumab must be permanently discontinued if the irAE does not resolve or the corticosteroid dose is not \leq 10 mg/day within 12 weeks of the last pembrolizumab treatment. The corticosteroid taper should begin when the irAE is \leq Grade 1 and continue at least 4 weeks. If pembrolizumab has been withheld, pembrolizumab may resume after the irAE decreased to \leq Grade 1 after corticosteroid taper. 			
Immune-related AEs	Toxicity grade (CTCAE V5.0)	Action with pembrolizumab	Corticosteroid and/or other therapies	Monitoring and follow-up
Pneumonitis	Grade 2	Withhold	Administer corticosteroids (initial dose of 1 to 2 mg/kg prednisone or equivalent) followed by taper Add prophylactic antibiotics for opportunistic infections	Monitor participants for signs and symptoms of pneumonitis Evaluate participants with suspected pneumonitis with radiographic imaging and initiate corticosteroid treatment
	Recurrent Grade 2, Grade 3 or 4	Permanently discontinue		

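### Two colitis instructions are internally inconsistent: the Grade 2 steroid taper against its own RXC004 restart condition (all modules), and the Grade 3 action in Module 3

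*Protocol*

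**What the plan says.** Colitis is managed through three tables in the protocol: Table 11 (Section 6.5.1), Table 19 (Appendix K) and Table 20 (Appendix L 1).

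**Grade 2.** Table 19 says "When symptoms have resolved, taper over 2-4 weeks". Later in the same cell, RXC004 may restart at a lower dose after resolution to Grade 1 or below and with "steroids tapered to physiological levels (<10 mg prednisolone per day equivalent dose) over at least 1 month". For pembrolizumab immune-related events, the general instructions of Table 20 have the taper begin at or below "Grade 1 and continue at least 4 weeks". Table 11 gives a steroid level for restart but no taper length.

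**Grade 3.** Table 11 first gives an interrupt-and-resume rule for RXC004. For combination patients it then adds "permanently discontinue both agents and manage as per Appendix K and Appendix L". Table 19 pauses RXC004 and, if applicable, pembrolizumab, gives the taper as "When symptoms improve, taper steroids to physiological levels over 4-8 weeks", and states "RXC004 can be restarted at a lower dose after colitis has resolved to Grade" 1 or below, with no exception for combination patients. Table 20 puts Grade 2 and Grade 3 together under withholding pembrolizumab and keeps permanent discontinuation for recurrent Grade 3 or for Grade 4.

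**Precedence.** Section 6.5.1 says that for patients on the combination "the most conservative guideline should be followed". Appendix K does not repeat this, and there is no counterpart for monotherapy.

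**The concern.** A site treating Grade 2 colitis can follow the taper sentence and then find that its patient does not meet the restart condition a few lines below. A site treating Grade 3 colitis in Module 3 reads a permanent stop in Table 11 and is sent on to two tables that describe a temporary hold.

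These rows are likely to be used. Section 12.3.1 names colitis as the exception to otherwise non-overlapping toxicity, and Section 2.3.1.2 makes it an adverse event of potential interest. Section 2.3.1.2 also reports Grade 3 events in 1 of 12 patients in RXC004/0002 and 1 of 21 in this study.

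Different readings change whether and when a patient restarts. They also change reported results. Interruptions, reductions and discontinuations are a stated safety endpoint (Protocol Section 3) and are tabulated under SAP 4.12.1. Under SAP 4.10, RXC004 relative dose intensity divides cumulative dose by the days from first to last dose times the planned dose. A patient who pauses and restarts therefore carries undosed days in the denominator. For a patient who stops for good, the denominator ends at the last dose. The same clinical event can thus be counted differently from site to site.

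**Working it through.** No sample size, power or error rate is involved, and the plan states no figure to reproduce. The check sets the passages side by side and compares the intervals in days.

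**1. Grade 2 taper.**

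| Source | Text | In days |
|---|---|---|
| Table 19, Grade 2, taper sentence | 2-4 weeks | 2 × 7 = 14 to 4 × 7 = 28 |
| Table 19, Grade 2, restart condition | at least 1 month | ≥ 28 (month as four weeks) or ≥ 28-31 (calendar month) |
| Table 20, general instructions | at least 4 weeks | ≥ 4 × 7 = 28 |

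- Taper sentence against restart condition: 14-28 meets ≥ 28 at the single value 28 if a month is four weeks (or a 28-day February). Otherwise there is no common value.
- Taper sentence against Table 20: the single common value is 28.
- Of the 28 − 14 + 1 = 15 whole-day lengths that the taper sentence permits, the 14 from day 14 to day 27 fail both other requirements on every reading. Day 28 satisfies Table 20, and satisfies the restart condition on the four-week reading.

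**2. Grade 3 taper, as a control.** Table 19 gives 4-8 weeks, that is 28-56 days. This lies wholly within ≥ 28 days, so it does not conflict with Table 20. The taper problem is confined to the Grade 2 cell and its relation to Table 20.

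**3. Grade 3 action, by treatment.**

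| | Table 11 | Table 19 | Table 20 |
|---|---|---|---|
| RXC004, monotherapy | interrupt; resume lower after resolution and taper | pause; restart lower after resolution and taper | not covered |
| RXC004, Module 3 | permanent stop | pause; restart lower allowed | not covered |
| Pembrolizumab, Module 3 | permanent stop | pause | withhold; permanent stop only if recurrent Grade 3, or Grade 4 |

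The monotherapy row is consistent. In Module 3 the split is two-way, permanent stop against temporary hold. For RXC004 it lies between Tables 11 and 19. For pembrolizumab it lies between Table 11 on one side and Tables 19 and 20 on the other.

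**4. Reach of the precedence rule.** It applies to combination patients. It therefore covers every patient affected by the Grade 3 conflict, but none of the Module 1 and 2 patients affected by the Grade 2 conflict.

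**5. Related differences in the same text.**
- The steroid level for restarting RXC004 is ≤ 10 mg/day prednisolone equivalent in Section 5.6.3.1 and Table 11, but < 10 mg/day in Table 19.
- The 12-week limit runs from the start of steroids in Table 19, but from the last pembrolizumab treatment in Table 20.

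**The case against.** The strongest reply is that Section 6.5.1 already deals with Grade 3. The conflict exists only in combination patients, the rule is written for combination patients, and between a permanent stop and a temporary hold the more conservative action is not in doubt. Table 19 is also permissive about restart, so a site that stops both agents breaches nothing in it. This largely stands. A reader might infer that sites cannot comply with Table 11, Appendix K and Appendix L together, or that Grade 3 restart is contradictory throughout the study. The documents do not support either reading: the precedence rule gives Module 3 an answer, and for Modules 1 and 2 Tables 11 and 19 agree. Nor is Table 20 a party to any dispute about restarting RXC004, since its action column concerns pembrolizumab.

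On the taper, a reader might infer that the two intervals never overlap and that no patient could ever qualify for restart. That is also too strong. The intervals can meet at day 28. In addition, the Grade 2 cell foresees longer steroid courses: the dose may go up again if symptoms return during the taper, and a patient without improvement in 72 hours is treated as Grade 3, with a 4-8 week taper. One could also read the longer taper as applying only when restart is planned, but the text does not say so.

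The precedence rule helps less on taper length, even in Module 3. Section 5.6.3.1 restricts corticosteroids as immunosuppressive or a possible cause of secondary osteoporosis, and bone toxicity is itself an event of potential interest. The documents do not say whether a longer or a shorter taper counts as conservative.

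Finally, the impact is not quantified. The one Grade 3 colitis event reported in this study was at 2 mg once daily, a monotherapy dose, where the Grade 3 instructions agree. No effect on a primary endpoint is shown, and PFS is counted whether or not the patient stays on study treatment. That stands, and it limits the weight of the point.

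**Conclusion.** The point holds in two limited parts.

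- **Grade 2, all modules.** The taper sentence and the restart condition in Table 19 agree at most at day 28. Tapers of 14-27 days follow the first and fail the second and, in Module 3, also fail Table 20. Nothing in the protocol resolves this for Modules 1 and 2.
- **Grade 3, Module 3 only.** Table 11 orders a permanent stop and refers to two tables that describe a temporary hold. The precedence rule largely settles what to do but leaves the conflicting text in force.

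The size is that of a wording defect in operative safety rules. It bears on restart decisions and on the interruption and discontinuation counts, and the number of patients affected cannot be derived from the documents. The conclusion assumes that a month means four weeks or a calendar month, and that the three tables are meant to be read together, as Section 6.5.1 and Table 11 direct. It takes no view on which clinical rule is right.

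**What to change.** Amend the protocol wording as follows, with the choice of clinical rule left to the sponsor's clinical team:

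- In Table 19, Grade 2, reconcile the taper sentence with the RXC004 restart condition, and with the taper minimum in Table 20 for Module 3. If the two durations are meant for different situations, say so.
- Align the Module 3 Grade 3 wording across Table 11, Table 19 (both agents) and Table 20 (pembrolizumab).
- At the same time, reconcile the ≤ 10 mg and < 10 mg restart thresholds and the two start points of the 12-week limit.

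The cost is text changes in Table 11 and Appendices K and L, with Section 5.6.3.1 if the threshold changes. No sample size, endpoint definition or SAP analysis needs to change.
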